1.3 RATIONALE FOR DEVELOPMENT OF STUDY DRUG IN DISEASE/CONDITION

Prostacyclin is a potent endogenous vasodilator and inhibitor of platelet aggregation. A synthetic salt of prostacyclin (ie, Flolan) has been previously shown to prolong survival in patients with PAH (Barst 1996). However, due to its very short half-life and chemical instability, Flolan has to be continuously infused by IV delivery. Treprostinil sodium is a chemically stable, longer acting analogue that has shown clinical effectiveness when administered by SC, IV (Remodulin, Remodulin Package Insert 2014], or inhaled routes (Tyvaso, Tyvaso Package Insert 2017).

Parenteral prostacyclins are considered by many providers as the “gold standard” for treatment of PAH; however, they are typically used later in the course of the disease due to the risks and difficulties associated with administration. Consequently, physicians managing patients with PAH commonly initiate treatment with an approved oral monotherapy to allow patients to benefit from the simplicity of an oral dosage form.

An innovative salt form, treprostinil diethanolamine, has been developed to deliver prostacyclin therapy via the oral route in a solid dosage form. Because the bioactive species is the same, treprostinil diethanolamine is expected to retain a similar safety and efficacy profile as parenteral treprostinil sodium in the convenience of an oral dosage form. It has been suggested that combination therapy, particularly with a prostacyclin, may prevent or delay the progression of the disease and thereby prolong the time to clinical worsening.

1.4 CLINICAL HYPOTHESIS

This open-label study will evaluate the safety of continued therapy with UT-15C in subjects who have completed TDE-PH-310. This study will provide long-term, open-label data regarding the safety and efficacy of UT-15C for the treatment of PAH.

The hypothesis for the frequency of dosing change from BID to TID is that delivering more sustained concentrations of treprostinil may allow for systemic exposure to drug that more closely resembles the approved parenteral product, Remodulin, and reduces the occurrence of prostacyclin AEs previously seen with the BID regimen. Both of these improvements may allow study subjects to titrate to a more effective UT-15C dose and thus study drug may show a clinically and statistically significant difference compared to placebo in delaying time to first clinical worsening and improving exercise capacity at Week 24.

2 OBJECTIVES

2.1 PRIMARY OBJECTIVE

The primary objective of this study is to provide UT-15C SR tablets for eligible subjects who participated in TDE-PH-310.

2.2 SECONDARY OBJECTIVES

Secondary objectives of this study are:

- To assess the long-term safety of UT-15C
- To assess the effect of continued long-term therapy with UT-15C on exercise capacity (6MWD/Borg dyspnea score), WHO Functional Class, and plasma concentrations of NT-proBNP (Week 48 only)

2.3 EXPLORATORY OBJECTIVE

Optional evaluation of pharmacogenomics

3 EXPERIMENTAL PLAN

3.1 STUDY DESIGN

This is an open-label study. Subject visits will occur at Baseline, Weeks 6 and 12, and every 12 weeks thereafter. The study will continue until either oral UT-15C becomes available within the respective territories or the study is discontinued by the Sponsor.

3.2 OVERALL SCHEDULE OF TIMES AND EVENTS

Study Timeline	Baseline ^b (Study Entry)	Week 6 ^c	Week 12 ^c	Follow-up Visits (every 12 weeks) ^c	Study Termination Visit ^k
Informed consent	X				
Inclusion/exclusion criteria	X				
Vital signs ^a	X	X	X	X	X
Physical examination	X				X
6MWT / Borg dyspnea score ^d	X	X	X	X	X
WHO Functional Class	X	X	X	X	X
Clinical laboratory assessments	X		X	X ^e	X
Urine pregnancy test ^f	X	X	X	X	X
Dose titration	X	X	X	X	
NT-proBNP	X			X ^g	
Drug accountability/ Compliance	X	X	X	X	X
AEs	X ^h	X	X	X	X ⁱ
Concomitant medications	X	X	X	X	X
Phone calls ^j	X	X	X	X	X
Pharmacogenomic Sample (Optional)				X ^l	X ^l

Abbreviations: 6MWT, 6-Minute Walk Test; AE, adverse event; NT-proBNP, N-Terminal pro-brain natriuretic peptide; WHO, World Health Organization

^a Vital signs should be conducted following at least 5 minutes of rest and prior to or at least 30 minutes following the corresponding 6MWT.

^b Baseline/study entry assessments (6MWT/Borg dyspnea score, WHO Functional Class, clinical laboratory parameters, NT-proBNP, vitals, and physical examination) for this study are those collected at the Study Termination Visit from Study TDE-PH-310 and prior to initiation of open-label study drug. Informed consent and inclusion/exclusion criteria are exclusive to this Protocol.

^c Visit windows are ±14 days.

^d 6MWT must be conducted 3 to 6 hours after the last dose of UT-15C. Subject should rest for 5 minutes prior to each 6MWT.

^e During the follow-up visits, clinical laboratory samples should be collected at the first Follow-up Visit and every other Follow-up Visit thereafter.

^f If applicable, for women of child-bearing potential (WOCBP).

^g NT-proBNP should only be collected at the Follow-up Visit # 3 (Week 48).

^h Any AEs that are ongoing at the Study Termination Visit from Study TDE-PH-310 should be recorded as continuing AEs in this open-label study.

ⁱ Any AEs that are ongoing at the Study Termination Visit from Study TDE-PH-311 should be followed for up to 30 days after completion of the Study Termination Visit.

^j Phone calls to the subject should occur at least weekly for the first 12 weeks, and at least monthly thereafter.

^k After the Study Termination Visit is completed, subjects should down titrate the study drug over an appropriate period of time in accordance with their clinical condition. Once the study drug has been discontinued, any remaining supplies should be returned to the clinic for drug accountability.

^l For subjects consenting to the optional pharmacogenomic sample. The sample should be collected at the next scheduled Follow-up Visit when clinical labs are also collected. If the subject discontinues prior to the next Follow-up Visit, pharmacogenomic samples should be collected at the Study Termination Visit.

3.3 CLINICAL ASSESSMENTS

3.3.1 *Efficacy*

3.3.1.1 *Six-Minute Walk Test*

A 6MWT (described in Appendix 15.1) will be conducted at Baseline as part of Study Termination assessments from Protocol TDE-PH-310, Week 6 and Week 12, every 12 weeks thereafter, and at the Study Termination Visit. Before each 6MWT, the subject should rest (seated) for at least 5 minutes. The 6MWTs will be conducted by qualified, trained personnel in a designated 6MWT area which meets the requirements outlined in Section 15.1. The 6MWT should be conducted approximately 3 to 6 hours after the last dose of UT-15C.

3.3.1.2 *Borg Dyspnea Score*

The Borg dyspnea score will be assessed following each 6MWT. The Borg dyspnea score is a 10-point scale rating the maximum level of dyspnea experienced during the 6MWT (Appendix 15.1). Scores range from 0 (for the best condition) to 10 (for the worst condition).

3.3.1.3 *WHO Functional Class*

The WHO Functional Class for PAH (Appendix 15.2) will be assessed at Baseline as part of Study Termination assessments from Protocol TDE-PH-310, Week 6, Week 12, every 12 weeks thereafter, and at the Study Termination Visit.

3.3.1.4 *N-terminal proBNP*

Plasma NT-proBNP concentration is a useful biomarker for PAH as it is associated with changes in right heart morphology and function (Fijalkowska 2006). The NT-proBNP sample collection will occur at Baseline as part of Study Termination assessments from Protocol TDE-PH-310 and at Follow-up Visit #3 (Week 48) only.

3.3.1.5 *Optional Pharmacogenomics*

For subjects consenting to pharmacogenomic analysis, blood samples will be collected at the first possible Follow-up Visit when clinical labs are also collected. If the subject discontinues prior to their next Follow-up Visit, pharmacogenomic samples will be collected at the Study Termination Visit. Pharmacogenomic samples will be shipped to the central laboratory for processing and storage prior to analysis. Genetic variants will be analyzed to evaluate their

association with observed clinical response during the blinded Study TDE-PH-310 and tolerability to prostacyclin therapy. Subjects who do not wish to participate in the optional pharmacogenomic research may still participate in the clinical study.

3.3.2 Safety

3.3.2.1 Vital Signs

Vital signs will be assessed at Baseline as part of Study Termination assessments from Protocol TDE-PH-310 and at all subsequent protocol-required visits. All vital signs will be collected prior to or at least 30 minutes following the corresponding 6MWT. Vital signs include blood pressure, peripheral (radial/brachial artery) heart rate, respiration rate, and weight. Vital signs must be collected following at least 5 minutes of rest to ensure accurate measurement.

3.3.2.2 Physical Examination

A physical examination will be assessed at Baseline as part of Study Termination assessments from Protocol TDE-PH-310 and at the Study Termination Visit.

3.3.2.3 Clinical Laboratory Assessments

Clinical laboratory parameters will be assessed at Baseline/Study Entry as part of Study Termination assessments from Protocol TDE-PH-310. Clinical laboratory assessments will also be assessed at Week 12, at every other Follow-up Visits thereafter, and at the Study Termination Visit. Clinical laboratory parameters to be assessed at the study visits are listed in Appendix 15.4. A urine pregnancy test will be collected at every visit for women of childbearing potential (WOCBP).

3.3.2.4 Adverse Event Assessments

Any AEs that are ongoing at the Study Termination Visit from Study TDE-PH-310 should be recorded as continuing AEs in this open-label study. Section 9 and Appendix 15.4 provide the guidelines and definitions for recording AEs.

All AEs will be captured from the time the informed consent form (ICF) is signed. All AEs should be followed until resolution (or return to normal or Baseline values), until they are judged by the Investigator to no longer be clinically significant, or for up to 30 days if the AE

extends beyond the final visit. All serious adverse events (SAEs) should be followed until resolution, death, or the subject is lost to follow-up even if they are ongoing more than 30 days after completion of the final visit. Sections 9 and Appendix 15.4 provide the guidelines and definitions for recording AEs.

Symptoms of PAH (disease-related events) should only be recorded as an AE if the event is either serious, new, or unusual with respect to intensity, frequency, duration as compared to symptoms in the subject's medical history, or there is a reasonable possibility that the event was caused by the study drug.

3.3.2.5 Concomitant Medications

Concomitant medication may be adjusted as deemed clinically necessary by the Investigator during the study. However, additional prostanoid therapies should not be permanently added. Concomitant medications used during the study will be reviewed at each protocol-required visit and recorded as they are prescribed in the Electronic Case Report Form (eCRF). Concomitant medications that were ongoing at the end of the TDE-PH-310 Study will be recorded in the eCRF for the open-label study.

3.4 NUMBER OF CENTERS

The centers who participate in Study TDE-PH-310 (approximately 150) will take part in the study.

3.5 NUMBER OF SUBJECTS

Up to 850 subjects from TDE-PH-310 may be eligible to participate in the study.

3.6 ESTIMATED STUDY DURATION

The study will continue for approximately 6 years. The study may be discontinued at any time if, in the opinion of the Investigators and/or Sponsor, continuation of the study represents a serious medical risk to the subjects. This may include, but is not limited to, the presence of serious, life-threatening, or fatal AEs, or AEs that are unacceptable in nature severity, or frequency. The Sponsor reserves the right to discontinue the study for any reason at any time. Subjects that discontinue the study will be contacted approximately 30 days (± 5 days) after study drug discontinuation to confirm their survival status. Subjects may also continue to be

contacted after the final study visit to assess AEs/SAEs (see Section 9.2 for additional details).

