4 SUBJECT ELIGIBILITY

4.1 INCLUSION CRITERIA

A subject is eligible to participate in this study if all of the following criteria apply:

1. The subject voluntarily provides informed consent to participate in the study.
2. The subject participated in Study TDE-PH-310 and met the definition of clinical worsening (as specified in Protocol TDE-PH-310), remained on study drug, was compliant with study procedures and assessments during the TDE-PH-310 Study or was currently enrolled in that study at the time the study was discontinued by the Sponsor.
3. All WOCBP must practice true abstinence from intercourse when it is in line with their preferred and usual lifestyle, or use 2 different forms of highly effective contraception for the duration of the study, and for at least 30 days after discontinuing study medication. Medically acceptable forms of effective contraception include: (1) approved hormonal contraceptives (such as birth control pills), (2) barrier methods (such as a condom or diaphragm) used with a spermicide, (3) an intrauterine device, or (4) partner vasectomy. For women of childbearing potential, a negative urine pregnancy test is required at Baseline (study entry) prior to initiating study medication. WOCBP includes any female who has experienced menarche and who has not undergone successful surgical sterilization (hysterectomy, bilateral tubal ligation, or bilateral oophorectomy) or is not postmenopausal (defined as amenorrhea for at least 12 consecutive months).
4. Males participating in the study must use a condom during the length of the study, and for at least 48 hours after their last dose of study medication.

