7.1.5 Study Termination Visit

When subjects discontinue the study, they will complete a Study Termination Visit. If possible, each subject should remain on study drug until they have completed the Study Termination visit. After the Study Termination Visit is completed, subjects should down titrate the study drug over an appropriate period of time in accordance with their clinical condition. Once the study drug has been discontinued, any remaining study drug should be returned to the clinic for drug accountability. The following assessments will take place at the Study Termination visit:

- Vital signs (following at least 5 minutes of rest)
- Physical examination
- WHO Functional Class
- AE assessment (for AEs ongoing at the Study Termination Visit, assessments to continue for up to 30 days beyond the Study Termination Visit)
- 6MWT/Borg dyspnea score (if possible, the 6MWT is to be initiated 3 to 6 hours after the last dose of UT-15C; Borg dyspnea score to be conducted immediately following 6MWT)
- Urine pregnancy test (for WOCBP)
- Clinical laboratory assessments
- Drug accountability/compliance
- Concomitant medications
- Collection of blood sample for evaluation of pharmacogenomics (optional) *

** If a subject discontinues prior to their next Follow-up Visit, pharmacogenomic samples will be collected at the Study Termination Visit.*

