9.4 PREGNANCY

If a study subject becomes pregnant during participation in this clinical study, site staff must notify the Sponsor within 24 hours of learning of the pregnancy by completing the Pregnancy Notification Form and either faxing or emailing this form to Global Drug Safety at United Therapeutics Corp. (+ 1 [contact] [U.S./Japan] or [name] [Europe/ROW]) or [contact]). Subjects who become pregnant during the study will be withdrawn

from active participation in the study and will discontinue study drug after an appropriate period of down-titration.

United Therapeutics Global Drug Safety Department will follow up with the Investigator to ensure appropriate data are provided regarding the outcome of the pregnancy, and to request that the Investigator complete a Pregnancy Outcome Report Form. Pregnancy only becomes an AE/SAE if there is an abnormal outcome, a spontaneous abortion, a termination for medical reasons other than PAH, or a congenital anomaly in the offspring.

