11.3 DEATHS

All deaths will be listed (including those occurring within 30 days of the last UT-15C dose) by subject, and will include the subject number, treatment group in the parent study, date of assessment (day), whether subject died, date of death (day), and cause of death (including other, specify text [if applicable]). An additional listing of deaths will include the subject number, first UT-15C dose in TDE-PH-311 study, last UT-15C dose (day) in TDE-PH-311 study, date of death (day), and cause of death. The summary of deaths will be presented by the parent study and overall and will include the number (percent) of subjects who died (including those within 30 days of study participation) and their causes of death.

Time to death will be calculated as:

(the death date – the date of the first UT-15C dosing in TDE-PH-311 study)

The Kaplan-Meier (K-M) estimator will be provided for the time to death, and K-M plots will be provided by treatment group in the parent study.

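### The one dated contact after the drug ends may fall before day 30 and asks only about survival, and no end date is set for pregnancy reporting; small gaps, cheaply closed

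*Protocol*

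**What the plan says.** **Contact after drug.** Protocol 3.6 says that subjects who discontinue will be "contacted approximately 30 days (± 5 days) after study drug discontinuation to confirm their survival status". The same section adds that they may also be "contacted after the final study visit to assess AEs/SAEs". That further contact is optional and has no date.

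**Deaths.** SAP 11.3 states: "All deaths will be listed (including those occurring within 30 days of the last UT-15C dose". The summary of deaths in the same section describes its 30 days differently: "including those within 30 days of study participation".

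**Pregnancy.** Protocol 4.1, criterion 3, requires contraception in women of childbearing potential "for the duration of the study, and for at least 30 days after discontinuing study medication". Urine tests are done at visits (3.2, 3.3.2.3, Appendix 15.3), and the last is at the Study Termination Visit. The 24-hour notification duty in 9.4 opens with "If a study subject becomes pregnant during participation in this clinical study" and gives no end date after drug.

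**Order of the last visit and the end of drug.** Section 7.1.5 says that, if possible, "each subject should remain on study drug until they have completed the Study Termination visit", and places down-titration after the visit. Section 8.1 asks the investigator to carry out the termination evaluations after UT-15C treatment has ended.

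**The concern.** The documents name two 30-day periods after drug: one for deaths, one for contraception. The only dated contact can be made before either period has run out, and its required content covers just one of the two subjects.

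For deaths, a subject confirmed alive on day 25 is not known to be alive on day 30. SAP 8.2 imputes nothing, and SAP 11.3 has no rule for a subject contacted before day 30. Whether days 26 to 30 are observed then depends on when the site happened to call.

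For pregnancy, the protocol treats the 30 days after drug as relevant, and 1.2.2 reports teratogenic effects in rabbits at high doses. A site that follows the protocol exactly could still have no occasion to learn of a conception in that period. Long-term safety is a stated secondary objective, so both gaps bear on something the study sets out to describe.

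**Working it through.** The plan gives no figure to reproduce: there is no sample size calculation and no event target (Protocol 10.2, SAP 6).

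**Inputs**
- Contact at 30 ± 5 days after drug: Protocol 3.6.
- Deaths within 30 days of the last dose: SAP 11.3.
- At most 850 subjects: Protocol 3.5.
- Survival of 93.6%, 87.9% and 82.2% at 1, 2 and 3 years in TDE-PH-304: Protocol 1.2.4. These describe an earlier extension study and serve only for scale.

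**Deaths: uncovered days**
- Allowed call days: 30 − 5 = 25 to 30 + 5 = 35.
- Worst case, call on day 25: 30 − 25 = 5 days uncovered; 5/30 = 16.7%.
- Calls spread evenly over the 11 whole days 25 to 35 (assumption): 5/11 = 45% fall before day 30. Mean uncovered time = (5 + 4 + 3 + 2 + 1)/11 = 15/11 = 1.36 days; 1.36/30 = 4.5%.

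**Deaths: expected number in the uncovered days**
- Constant hazard h = −ln(0.936) = 0.0661 per year. Check: −ln(0.879)/2 = 0.0645 and −ln(0.822)/3 = 0.0653, so a constant rate fits the quoted survival figures.
- All N subjects called on day 25: N × [exp(−25h/365.25) − exp(−30h/365.25)].
- Evenly spread calls: N × h × 1.364/365.25.

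| Subjects who stop drug | All called on day 25 | Calls spread evenly |
|---|---|---|
| 850 (ceiling) | 0.77 | 0.21 |
| 200 (assumed) | 0.18 | 0.05 |

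For comparison, 850 × [1 − exp(−30h/365.25)] = 4.6 deaths would be expected over the whole 30 days. The table counts deaths that fall in the uncovered days. That is an upper bound on deaths missed, because some would reach the site by another route.

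**Pregnancy: the passages side by side**
- *Tests.* None is scheduled after the Study Termination Visit.
- *Order of the visit.* Under 7.1.5 the last test comes before down-titration, so the taper and the following 30 days have no test. Under 8.1 the last test comes after treatment, and only the part of the 30 days after that visit has none. The two sections cannot both be followed.
- *Required questions.* The dated contact in 3.6 asks about survival. Section 7.1.5 lists no telephone call after the visit.
- *Optional AE/SAE contact.* By 9.4, a pregnancy counts as an AE or SAE only with an abnormal outcome or one of the other listed events, so an AE question need not bring a normal pregnancy to light.
- *Notification.* Section 9.4 ties it to participation, which is not defined after the final visit. The pregnancy listing in SAP 11.4 likewise asks about pregnancy during the study.

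Moving the call from day 25 to day 35 changes none of these five points. The pregnancy gap comes from the content of the contact and the reach of 9.4, not from the call day.

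**Anchors for the 30 days.** SAP 11.3 uses both the last dose and study participation. Follow-up of ongoing AEs in Protocol 3.2 runs from the Study Termination Visit. These dates differ whenever a taper follows the visit.

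**The case against.** The case against giving this much weight is good, and most of it stands.

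- A symmetric window around a target day is an ordinary design choice. Contacts on days 30 to 35 leave nothing uncovered.
- Other routes exist. AE/SAE contact after the final visit is allowed, unused drug is returned to the clinic once treatment has ended, SAEs arising on study are followed to resolution or death, and any SAE is reportable within 24 hours once the site knows of it. These lower the chance of a miss. None is a required question on a fixed day after drug.
- SAP 11.3 lists all deaths, and its 30-day phrase is inclusive. A reader might infer that a 30-day mortality endpoint is being cut short. The SAP defines no such endpoint, and a later death that becomes known would still be listed.
- The period in 4.1, "for at least 30 days after discontinuing study medication", is a contraception requirement and not a reporting window. That is correct. The point is only that nothing in the follow-up matches a period the protocol itself marks out.
- The wording of 9.4 does not clearly exclude the taper. That is also fair: it is undefined there, which is a reason to define it.
- The study is descriptive, with no hypothesis testing (Protocol 10.3), so no inference turns on this.

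**Conclusion.** The point holds as a minor gap in ascertainment, in two separate parts.

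*Deaths.* Up to 5 of 30 days can go unconfirmed. With all 850 subjects stopping drug, that is about 0.2 deaths if calls are spread evenly and about 0.8 if every call is on day 25. Both figures assume that the TDE-PH-304 rate applies after drug has stopped. A reader might infer a larger loss by supposing a higher hazard after stopping: multiplying it by 3 or 5 gives about 2.3 or 3.8 deaths with every call on day 25. The synopsis warns that sudden dose reductions may worsen PAH, which suggests a direction, but the documents give no hazard after stopping, so those multiples have no support here.

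*Pregnancy.* Whatever the call day, no scheduled test or required question covers pregnancy through the 30 days after the last dose, and 9.4 has no stated end date after drug. The documents do not allow a count. A reader might infer that the whole taper plus 30 days is untested in every woman of childbearing potential. That follows from 7.1.5 but not from 8.1, so it is not established.

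Nothing here shows that events will be missed, only that a site can follow the plan exactly and miss them.

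**What to change.** - **Protocol 3.6:** place the existing contact on or after day 30 from the last dose, for example days 30 to 40, and add a pregnancy question for women of childbearing potential.
- **Protocol 9.4:** extend the notification period through 30 days after the last dose of study drug, including down-titration.
- **SAP 11.3:** use one anchor for the 30 days, either the last dose or study participation, in both the listing and the summary. The last dose would match the contact in 3.6.
- **Protocol 7.1.5 and 8.1:** reconcile the two on whether the termination evaluations come before or after the end of treatment.

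The cost is a few lines of text and one question in a call that is already required, with no added visit or test. There are two downsides. The call falls a few days later, and a question without a test may miss a very recent conception. Priority: minor; a cheap improvement.
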